1. PROCEDURE

The research consists on studying the effects of tDCS in combination with cognitive behavioural therapy (CBT) in adults diagnosed with gambling disorder that attend the UK National Problem Gambling Clinic. The design of the study consists on a double blind randomized control interventional trial with parallel assignment (two interventions – tDCS in combination with CBT that will be evaluated against CBT alone).

Participants will be split in two groups depending on the treatment they receive. The treatment groups will be: tDCS real stimulation with CBT or tDCS sham with CBT. Real stimulation condition involves the application of tDCS stimulation for 20 minutes whereas sham condition is used as a control (similar to a placebo).

The investigators aim to have a total of 32 participants diagnosed with gambling disorder based on the Problem Gambling Severity Index (PGSI). There will be 16 participants per condition, having two conditions (real stimulation and sham).

Treatment 1. Participants will attend 8 weekly sessions where they receive tDCS real stimulation while complete CANTAB cognitive tasks to measure cognitive functions and following this, they will attend a CBT session.

Treatment 2. Participants will attend 8 weekly sessions where they receive sham tDCS, while complete CANTAB cognitive tasks to measure cognitive functions and following this, they will attend a CBT session.

Primary endpoint/outcomes

1. Change in scores on the Yale-Brown Obsessive Compulsive Scale adapted for Pathological Gambling (PG-YBOCS). [Time Frame: Change from baseline PG-YBOCS scores at week 2, 3, 4, 5, 6, 7 and 8].
2. Change in scores on the Visual Analogue Scale (VAS). [Time Frame: Change from baseline VAS scores at week 2, 3, 4, 5, 6, 7 and 8].
3. Change in scores on the Gambling Symptom Assessment Scale (G-SAS). [Time Frame: Change from baseline G-SAS scores at week 8].
4. Change in scores on the Cambridge Gambling Task (CGT). [Time Frame: Change from baseline CGT scores at week 8].

Secondary endpoints/outcomes

1. Change in scores on the Information Sampling Task (IST). [Time Frame: Change from baseline IST scores at week 2, 3, 4, 5, 6, 7 and 8].

2. Change in scores on the Stop Signal Task (SST). [Time Frame: Change from baseline IST scores at week 2, 3, 4, 5, 6, 7 and 8].
3. Changes in encephalography (EEG) neural oscillatory activity. [Time Frame: Correlation of tDCS and EEG activity in weeks 1, 2, 3, 4, 5, 6, 7 and 8].

Primary objective

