The main objective is to study whether 8 weekly sessions during 8 consecutive weeks of tDCS simulation will help to decrease cravings and addiction symptoms such as risk-taking behaviour and impulsivity in patients diagnosed with gambling disorder attending the UK National Problem Gambling Clinic, exploring whether tDCS combined with CBT will improve the treatment outcomes – reducing significantly more the symptomatology, compared to CBT treatment alone.

Hypothesis 1:

Null hypothesis (H_0): The primary outcome measures results will be the same in the group of participants that receive tDCS real stimulation combined with CBT and the control group (sham tDCS + CBT).

Alternative hypothesis (H_A): The primary outcome measures results will not be the same in the group of participants that receive tDCS real stimulation combined with CBT and the control group (sham stimulation + CBT).

Hypothesis 2:

H_0 : The primary outcome measures results obtained in the baseline will be the same to the outcome measures results at the end of the treatment.

H_A : The primary outcome measures results obtained in the baseline will not be the same to the outcome measures results at the end of the treatment.

Secondary objectives

To investigate if electrophysiological measures (EEG resting state) predict behavioural outcomes obtained from the cognitive task performance during tDCS experiments, as well as studying the task performance progression comparing every week's results to the baseline.

Hypothesis 1:

H_0 : The secondary outcome measures results obtained from the EEG resting state will be the same in the group of participants that receive tDCS real stimulation combined with CBT and the control group (sham tDCS + CBT).

H_A : The secondary outcome measures results obtained from the EEG resting state will not be the same in the group of participants that receive tDCS real stimulation combined with CBT and the control group (sham tDCS + CBT).

Hypothesis 2:

H_0 : The secondary outcome measures results obtained in the baseline will be the same to the outcome measures results at the end of the treatment.

H_A : The secondary outcome measures results obtained in the baseline will not be the same to the outcome measures results at the end of the treatment.

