5. STATISTICAL ANALYSIS PLAN

Data source

Behavioural data sets will be obtained from computer-based cognitive tasks and questionnaires that participants complete during the stimulation sessions. The results obtained from completing these tasks and questionnaires generate measures for addiction-related symptoms such as cravings, impulsivity, risk-taking behaviour, delay aversion and control inhibition. Each participant will produce data at two time points for G-SAS and CGT measures and at eight time points for VAS, PG-BOCS and secondary measures. Electroencephalography (EEG) resting state neural oscillatory activity will be recorded for 5 minutes prior and 5 minutes after the tDCS intervention.

Analysis objectives

The investigators will study whether the behavioural and cognitive data obtained from participants in different time points are significantly different between the two treatment groups. In addition, the investigators will investigate if electrophysiological measures (EEG resting state) predict behavioural outcomes obtained from the cognitive task performance during tDCS experiments, as well as studying the task performance progression comparing every week's results to the baseline.

Analysis sets/Subgroups

The following data sets subgroups will be analysed:

1. Experimental - Stimulation with CBT: Participants that attend to 8 weekly sessions of tDCS stimulation and that following the tDCS session, they attend to a cognitive behavioural therapy (CBT) session.
2. Sham Comparator - Sham with CBT: Participants that attend to 8 weekly sessions of sham tDCS and that following the tDCS session, they attend to a CBT session.

The aim is to study whether the combination of stimulation and therapy help to improve the treatment outcomes in comparison with CBT alone.

Variables and covariates

Primary Dependent Variables:

1. Pathological Gambling adapted Yale-Brown Obsessive Compulsive Scale (PG-YBOCS) scores for gambling severity.
2. Visual Analog Scale (VAS) scores for gambling cravings.
3. Gambling Severity Symptoms Assessment (G-SAS) for gambling symptoms.
4. Cambridge Gambling Task's (CGT) scores for gambling behaviour.

Secondary Dependent Variables:

1. Stop signal task's (SST) scores for inhibition control.
2. Information Sampling Task's (IST) scores for impulsivity.
3. EEG resting state oscillatory neural activity.

Independent Variables:

1. tDCS condition (Stimulation or Sham)
2. Time (sessions 1 to 8)

Covariates:

1. Age
2. Gender

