Handling of missing values

We expect to have very few cases of missing values due to the methodology used in the study. The variables will be measured with a computer software that doesn't allow to continue with the test unless one of the options is selected. The only possible missing values would come by an error on the whole task, which will result in no data at all. In this case, we would withdraw this participant from the analysis of that specific task.

The possible missing values that we would expect to deal with, will come from the covariates measures that are obtained from paper-based questionnaires. The researcher checks before the participant leaves the session that they have completed all the questions. However, if we have to deal with missing values, we will use common-point imputation that is commonly used for rating scales, which is the case in our questionnaires. With this technique we would use the most commonly chosen value for the rest of the questions and substitute it for the missing value

Statistical Procedures

The analysis performed will be as in Loo et al (2012): the two treatment groups will be analysed for differences in demographic and clinical variables at baseline using χ^2 -tests for categorical variables

and t-tests for continuous variables. To test the effect of tDCS on test performance, a 2 x 2 mixed between-within ANOVA will be conducted. The between-groups factor will be stimulation condition (real stimulation vs sham) and the within-participants factor will be time (change from baseline). Analyses will test for main effects of stimulation condition and session as well as the stimulation-session interaction.

Secondary measures involve cognitive tasks and EEG resting state neural oscillations recording. Differences between sessions scores will be analysed with mixed between-within repeated measures ANOVA. The between-groups factor will be tDCS condition (real tDCS vs sham tDCS) and the within-participants factor will be time (change from baseline). Analysis will test for main effects of group (tDCS condition) as well as for tDCS-time interaction to investigate the presumable accumulative effects of tDCS. This analysis will serve to study if specific EEG resting state oscillatory activity correlates with the modulatory effect of tDCS on task performance and to explore the presumable accumulative effect of tDCS across time.

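### The single 2 x 2 ANOVA does not fit the eight-session primary outcomes PG-YBOCS and VAS; age and gender enter no stated model, and the EEG-prediction objective has no model with EEG as a predictor

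*Combined protocol and SAP*

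**What the plan says.** Section 5, Statistical Procedures, first describes baseline comparisons by chi-square and t-tests and then gives the efficacy test: "To test the effect of tDCS on test performance, a 2 x 2 mixed between-within ANOVA will be conducted". Its factors are stimulation condition and time, with time glossed as change from baseline; the two time levels are not listed. Both main effects and their interaction are to be tested. The text then turns to the secondary measures, for which it plans a mixed repeated-measures ANOVA of unstated dimension.

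Section 5, Data source, says that each participant contributes data "at two time points for G-SAS and CGT measures and at eight time points for VAS, PG-BOCS and secondary measures". Under Variables and covariates, time runs over all eight sessions, and age and gender are listed as covariates.

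Section 1, Primary endpoint/outcomes, defines the endpoints as "Change from baseline PG-YBOCS scores at week 2, 3, 4, 5, 6, 7 and 8" and "Change from baseline VAS scores at week 2, 3, 4, 5, 6, 7 and 8". G-SAS and CGT each have one endpoint, at week 8. Primary Hypothesis 1 compares the arms and gives no time point. The null of primary Hypothesis 2 names no arms: "The primary outcome measures results obtained in the baseline will be the same to the outcome measures results at the end of the treatment".

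The secondary objective is "To investigate if electrophysiological measures (EEG resting state) predict behavioural outcomes obtained from the cognitive task performance during tDCS experiments". The formal EEG hypothesis beneath it is an arm comparison: "The secondary outcome measures results obtained from the EEG resting state will be the same in the group of participants" with active and with sham stimulation. Statistical Procedures says that the group-by-time ANOVA will also serve to examine how EEG correlates with the effect of tDCS on the tasks.

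**The concern.** With two arms, a 2 x 2 design has room for two time levels. PG-YBOCS and VAS, two of the four primary outcomes, have eight. A reader cannot tell whether the decisive test uses two sessions or eight, and these are different tests. If baseline and session 8 are meant, six of the eight sessions go unused and the endpoints at weeks 2 to 7 are not tested. If 2 x 2 is a slip for 2 x 8, the test needs a rule for non-sphericity that the plan does not give. In either case the choice could be made after the data are seen.

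Two further gaps sit in the same section. Whether the results will be adjusted for age and gender is left open. And the analysis offered for the EEG-prediction objective has condition and time as its only factors, so no term in it links a participant's EEG to that participant's task score.

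**Working it through.** **Inputs from the document.** N = 32, 16 per arm (section 2, Participants); G = 2 arms; T = 2 time points for G-SAS and CGT, and T = 8 for PG-YBOCS and VAS (section 5, Data source).

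**Step 1: which design fits which outcome.** In a mixed ANOVA the interaction df are (G-1)(T-1) and the error df are (N-G)(T-1).

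| Reading | T | Cells | Interaction df |
|---|---|---|---|
| Baseline and session 8 | 2 | 4 | 1, 30 |
| Changes at weeks 2-8 | 7 | 14 | 6, 180 |
| Sessions 1-8 | 8 | 16 | 7, 210 |

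The stated 2 x 2 is reproduced for G-SAS and CGT. It is not reproduced for PG-YBOCS and VAS under either many-session reading. Adding age and gender would lower the between-participant error df from 30 to 28.

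**Step 2: what the open choice costs.** The document gives no SD, correlation or effect size, so all of these are assumed: SD 1, complete data, two-sided 5%, compound symmetry (CS) at 0.3/0.5/0.7 and AR(1) at 0.5/0.7/0.9, and an effect growing linearly to 1 SD at week 8. There were 20,000 simulated trials per case.

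| | CS 0.3/0.5/0.7 | AR(1) 0.5/0.7/0.9 |
|---|---|---|
| Power, 2 x 2 (baseline, session 8) | 64/78/94% | 49/53/76% |
| Power, 2 x 8 interaction, Greenhouse-Geisser | 53/72/94% | 39/43/70% |
| One significant, the other not | 30/22/8% | 23/19/11% |
| No effect: either significant | 8.0/7.7/7.4% | 7.9/7.6/7.1% |
| No effect: uncorrected 2 x 8 | about 5% | 7.2/8.9/10.7% |

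The 2 x 2 row can be checked by formula. The interaction is a t-test on change, with SD √(2(1-r)) and noncentrality 1/[√(2(1-r)) × √(2/16)] on 30 df. For r = 0.5 this is 1/(1 × 0.354) = 2.83, power 78%. For AR(1) 0.5 the correlation between sessions 1 and 8 is 0.5^7 = 0.008, the noncentrality is 2.01 and the power is 49%.

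**Step 3: G-SAS and CGT.** Simulated power at a 1 SD effect, for baseline correlation 0.3/0.5/0.7: 2 x 2, 64/78/94%; ANCOVA with baseline, 80/87/96%; ANCOVA with baseline, age and gender, 77/85/95% when age and gender are not prognostic. All hold 5% under no effect.

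**Step 4: EEG.** No arithmetic applies. Prediction needs EEG on the right-hand side of a model for task score. In the variable list EEG is a dependent variable only, and the ANOVA contains condition and time only. It can test whether EEG differs between arms or changes from baseline, which are the formal hypotheses. It cannot estimate the relation between EEG and task score.

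**The case against.** The plan can be defended on several counts, and part of the defence stands.

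- **The 2 x 2 is valid for half the primary outcomes.** This is true: G-SAS and CGT have two time points. ANCOVA there is a gain in efficiency, not a correction, and with age and gender it is worth about one point of power at r = 0.7.
- **Hypothesis 2 points to baseline and end of treatment.** It suggests those two levels, but Statistical Procedures does not name them, and the endpoints and the time variable say otherwise.
- **The analysis follows a cited 2012 study.** That source is not available here, and it could not remove a conflict within the plan's own text.
- **The test refers to test performance, not to the primary outcomes.** If it excludes them, they have no stated test at all.
- **Listing covariates shows an intent to adjust.** It does, but the intent is not carried into a model.

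Some stronger readings are tempting and are not supported. A reader might take the 8-30% of trials in which the two tests disagree as the harm done by this defect. It means only that one p-value falls below 0.05 and the other above. In the same six cases the 2 x 2 and a week-8 baseline ANCOVA disagree in about 4-33% of trials, and reporting either gives 7-8% false positives for that pair too. Disagreement of this order is usual for two reasonable tests at this sample size.

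A reader might also infer weekly 2 x 2 tests (18-24% false positives per outcome if uncorrected), or an EEG regression that ignores session (32-79% under assumed drift). The plan contains neither analysis. These figures are warnings about what might be added later.

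**Conclusion.** The conflict is established from the document's own text. The only stated primary test does not match the eight sessions and the weeks 2-8 endpoints of PG-YBOCS and VAS, and the levels that would settle the matter are not given. Age and gender have no place in any stated model. The EEG-prediction aim has no analysis that can answer it, although the formal EEG hypotheses do.

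The size is moderate. Leaving the choice of test open raises the false-positive rate from 5% to 7-8% for each affected outcome, and an uncorrected 2 x 8 can reach about 11% under strong AR(1) correlation. These figures rest on assumed correlations and complete data. They do not support a reading that the whole primary analysis is invalid or that the data are unusable. This should be fixed in the SAP before the data are analysed.

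**What to change.** 1. **PG-YBOCS and VAS, arm comparison (Hypothesis 1).** Use a repeated-measures mixed model on sessions 2-8 with arm, session, arm x session, baseline, baseline x session, age and gender. State the covariance structure and the small-sample degrees of freedom, and name one arm contrast in advance. Week 8 is one option. Section 2, Trial procedures, places session-8 scores before that session's stimulation, so they follow seven stimulations, and the SAP should say so. If ANOVA is kept, write 2 x 8, add a sphericity correction and name the decisive contrast.
2. **G-SAS and CGT, arm comparison.** Replace the arm test of the 2 x 2 with ANCOVA of the week-8 score on arm, baseline, age and gender.
3. **Hypothesis 2.** The models in items 1 and 2 contain no baseline-to-end effect and would drop this hypothesis if used alone. Keep a separate test, such as the session effect of the 2 x 2 or a contrast of baseline with session 8, and state that it is not evidence for tDCS.
4. **EEG prediction.** Model task score on pre-stimulation EEG with arm, session, arm x session and a participant effect, and name the EEG measure in advance. SST is done during stimulation, so same-session EEG precedes it. IST is done before that session's EEG, so use the previous session's EEG or call the result an association.

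The cost is SAP wording and standard software, with no new visits, data or participants. Age and gender use two degrees of freedom: if not prognostic, they cost about 1.5 to 3.5 points of ANCOVA power (for example 96.3% to 94.8% at r = 0.7), which still leaves it at or above the 2 x 2.

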Consecutively, the researcher will set up of equipment and parameters (place the cap on the participant's head); apply tDCS stimulation (20 minutes) while participant complete cognitive computer based tasks; remove the cap to conclude the session.

- In session 1 and session 8 participant will complete the next questionnaires and cognitive task before the tDCS/EEG protocol:
 1. Gambling Severity Symptom Assessment Scale (G-SAS).
 2. Cambridge Gambling Task (CGT).
- In sessions 1, 2, 3, 4, 5, 6, 7 and 8 participants will complete the next questionnaires and cognitive tasks (tests 1-3 before tDCS/EEG protocol and task 4 during tDCS stimulation). EEG resting state will be recorded before and after tDCS:
 1. Yale-Brown Obsessive Compulsive Scale adapted for Pathological Gambling (PG-YBOCS)
 2. Visual Analogue Scale (VAS) for gambling cravings.
 3. Information Sampling Task (IST)
 4. Stop Signal Task (SST)
 5. EEG resting state recording

Randomization method

Simple randomization will be employed. This method is based on a single sequence of random assignments. Computer-generated random numbers will be used for simple randomization of subjects prior to the experiment start – assigning randomised numbers to the order in which participants sign up - to ensure equivalent numbers of participants per arm. This technique guarantees randomness of the assignment of a subject to a particular group.

Masking

Neuroelectrics tDCS software will be set up in double blind mode, which ensures that neither the investigator (who conducts the experimental session) nor the participant, will know the condition (real stimulation or sham) the participant has been allocated to. Participant allocation to each stimulation group will be randomized prior the study commences as stated above, and tDCS templates will be created for each participant, to ensure that they will remain during the 8 stimulation sessions in the same group.

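### The SAP does not say whether the stimulation main effect or the interaction decides Hypothesis 1, and the main effect is a diluted test of tDCS because it includes session 1

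*Combined protocol and SAP*

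**What the plan says.** Section 5 (Statistical Procedures) says that, to test the effect of tDCS, "a 2 x 2 mixed between-within ANOVA will be conducted". The between-groups factor is real stimulation or sham, and "the within-participants factor will be time (change from baseline" is how the other factor is described. The two levels of time are not named. The same paragraph continues: "Analyses will test for main effects of stimulation condition and session as well as the stimulation-session interaction". No term is singled out as the test of primary Hypothesis 1, which compares the arms on the primary outcomes.

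The measurement schedule settles the two levels for two of the four primary outcomes:

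- Section 5 (Data source): "Each participant will produce data at two time points for G-SAS and CGT measures".
- Section 2 (Trial procedures): "In session 1 and session 8 participant will complete the next questionnaires and cognitive task before the tDCS/EEG protocol".

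PG-YBOCS, VAS, IST and SST are collected at all eight sessions, with "tests 1-3 before tDCS/EEG protocol and task 4 during tDCS stimulation". PG-YBOCS and VAS at session 1 therefore also precede stimulation; the SST does not. Section 1 defines all four primary outcomes as change from baseline. Section 5 lists age and gender as covariates, but not the baseline score of the outcome.

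**The concern.** In a pre-post layout the group main effect compares the arms on each participant's average over the two occasions. One of those occasions is before the first stimulation, so tDCS cannot affect it. The result is a diluted estimate that also carries any chance difference between the arms at the start.

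The SAP lists this term beside the interaction without ranking them, so either could be reported as the answer to Hypothesis 1. If the main effect is used, a real benefit is more likely to be missed. In a trial whose arms happen to differ at session 1, the main effect may largely reflect that difference. With 32 participants, simple randomization and no adjustment for the baseline score, such gaps are to be expected.

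**Working it through.** **Inputs from the documents.** Two arms of 16 (section 1), which agrees with the stated total: 2 x 16 = 32. No power calculation is given, so there is nothing further to reproduce. G-SAS and CGT are taken at sessions 1 and 8 only, before that session's tDCS.

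**Assumptions not in the documents.** Two-sided alpha 0.05; true session-8 effect d (1.0 SD in the power table), scored so that positive is benefit; equal SDs at both sessions; correlation r between sessions 1 and 8, shown from 0 to 0.7; no dropout.

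**Expected values.** Let g be the observed session-1 gap (real minus sham, in SD). Given g, the expected session-8 difference is d + rg. Then:

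- Main effect: (g + d + rg)/2 = d/2 + g(1+r)/2
- Interaction (difference in change): d + rg - g = d - g(1-r)
- Session 8 adjusted for session 1: d + rg - rg = d

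Averaged over randomizations g is zero, so the main effect estimates d/2 and the other two estimate d. A simulation of 200,000 trials with d = 0.8 and r = 0.5 gave 0.400 for the main effect and 0.800 for the interaction.

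**Standard errors**, with 2/16 = 0.125:

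- Main effect: sqrt(0.125 x (1+r)/2)
- Interaction: sqrt(0.125 x 2(1-r))
- Adjusted: sqrt(0.125 x (1-r^2)), ignoring the small loss when the arms differ at session 1

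**Power for d = 1.0** (non-central t; 30 df, or 29 for the adjusted comparison):

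| r | SE main / interaction / adjusted | Power main / interaction / adjusted |
|---|---|---|
| 0 | 0.250 / 0.500 / 0.354 | 49 / 49 / 78% |
| 0.3 | 0.285 / 0.418 / 0.337 | 40 / 64 / 82% |
| 0.5 | 0.306 / 0.354 / 0.306 | 35 / 78 / 88% |
| 0.7 | 0.326 / 0.274 / 0.252 | 32 / 94 / 97% |

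**Effect of a chance gap.** The SE of g is sqrt(0.125) = 0.354 SD, so a gap of at least 0.5 SD in either direction has probability 2(1 - Phi(0.5/0.354)) = 15.7%. For g = 0.5 SD:

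| r | Shift in main effect, g(1+r)/2 | Shift in interaction, -g(1-r) |
|---|---|---|
| 0.3 | +0.325 | -0.35 |
| 0.5 | +0.375 | -0.25 |
| 0.7 | +0.425 | -0.15 |

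If the real arm starts 0.5 SD worse and d = 1.0, the expected main effect is 0.5 minus the first column of shifts: 0.175, 0.125 and 0.075 SD.

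**Type I error.** With d = 0 and r = 0.5, the simulated rejection rate of the main effect is 5.1% overall. Among trials with a gap near 2 SE (about 0.71 SD) it is about 30%, against about 12% for the interaction. Near 1 SE it is about 2%, against 5%.

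**PG-YBOCS and VAS.** If only sessions 1 and 8 enter, the dilution is again one half. If all eight enter, a constant effect from session 2 keeps (0 + 7 x 1)/8 = 7/8 of its size; a linear build-up from 0 at session 1 to d at session 8 keeps one half of d.

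**The case against.** The strongest reply is that the valid test is already in the quoted sentence. In this layout the interaction is the same as a t-test on change from session 1, and section 1 defines every primary outcome as a change from baseline. For secondary measures the SAP links accumulating tDCS effects to the tDCS-time interaction. Main effects are also routine output of a mixed ANOVA. This stands: a reader might infer that the plan has no sound test of tDCS, and the documents do not support that. What remains is that the whole ANOVA is introduced as the test of tDCS and no term is named as decisive.

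Four other points limit the claim.

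- **The label on the time factor.** It could mean change scores with baseline set to zero. The person average is then (0 + change)/2: the estimate is still halved, but so is its SE, so the test equals the interaction and no power is lost. A genuine factor of two post-baseline changes cannot be built for G-SAS or CGT, which have one change each. For raw scores, sessions 1 and 8 are the only possible levels.
- **The power loss depends on r.** At r = 0 the main effect and the interaction have equal power.
- **Baseline gaps would be seen.** The SAP plans baseline comparisons of clinical variables. It states no consequence for the model.
- **CGT timing.** Section 1 has CANTAB tasks completed during stimulation, while the session schedule in section 2 puts the CGT before it. The working follows the schedule; the two sections must be reconciled.

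**Conclusion.** The point holds as a ranking and efficiency problem. The SAP offers two tests of tDCS without choosing between them, and one is clearly weaker at any positive r. For G-SAS and CGT analysed as raw scores, the main effect estimates half the session-8 effect. Under the stated assumptions its power for a 1.0 SD effect is 49% to 32% as r goes from 0 to 0.7, against 49% to 94% for the interaction and 78% to 97% with baseline adjustment. Effect size, alpha and r are assumed.

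Three stronger readings are tempting and are not supported:

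- That every primary outcome is halved. Exact halving is certain only for G-SAS and CGT; for PG-YBOCS and VAS it depends on the sessions used and the course of the effect.
- That false positives are inflated. Under randomization the overall type I error stays nominal; the harm is dilution, and a misleading result given the gap actually observed.
- That relying on the interaction cures the baseline problem. It is shifted in the opposite direction, and at r = 0.3 by slightly more in absolute terms. Only adjustment for the session-1 score removes the shift.

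**What to change.** In section 5, Statistical Procedures:

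1. For G-SAS and CGT, name the between-arm difference at session 8, adjusted for the session-1 score (ANCOVA), as the test of primary Hypothesis 1.
2. For PG-YBOCS and VAS, use sessions 2-8 as outcomes and the session-1 score as covariate.
3. State that a stimulation main effect computed over data that include session 1 will not be interpreted as an effect of tDCS.

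The SST is outside this change, because the schedule places it during stimulation at session 1, so that value is not a pre-stimulation baseline.

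The cost is an edit to one SAP paragraph. The baseline scores are already collected; no visit, measurement or participant is added. Under the assumptions above, power rises at every r shown compared with either planned term.
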